**PI: [name].**

Self-Report Measures:

These measures will be administered via an iPad linked to UW's secure REDCAP database system.

*Data Collection Form:* internal form used to collect study specific information such as handedness, age, race/ethnicity, medications, etc.

*Beck Depression Inventory (BDI):* measures the severity of current depression (Beck et al., 1961).

*Childhood Trauma Questionnaire (CTQ):* measures histories of abuse and neglect during childhood (Bernstein, et al. 2003).

*Difficulty in Emotion Regulation Scale (DERS):* assesses multiple aspects of emotion dysregulation (Gratz & Roemer, 2004).

*Five Facet Mindfulness Questionnaire (FFMQ):* assesses the level of awareness over the inner experience (Baer et al., 2006).

*Mood and Anxiety Symptoms Questionnaire (MASQ):* measures general (non-disorder specific) symptoms of mood dysfunction and anxiety.

*Menstrual Cycle Information Log:* charts the length and regularity of the menstrual cycle and type and dosage of any birth control medications.

*Pittsburgh Sleep Quality Index (PSQI):* measure of the quality of sleep in the past month.

*Positive and Negative Affect Scale (PANAS):* measure of current (at this moment) affect (Watson et al., 1988).

*Posttraumatic Stress Disorder Checklist- 5 (PCL-5):* assesses the 20 DSM-5 symptoms of PTSD (Weather et al., 2013).

*Electrotactile Stimulation Calibration:* Explains and assess the targeted intensity of stimulation. Note: this measure is completed during fMRI scanning.

*Side Effect Checklist:* assesses possible side effects across multiple domains of functioning.

Neurocognitive measures:

*One-word receptive vocabulary test* (Brownell, 2000): a well-normed measure of verbal IQ.

**Version: 6**

**Date: 09/09/15**

**Page: 8**

*Digit span subscale of WAIS-IV:* measures working memory capacity.

*Spatial cueing task:* the spatial cueing task (e.g., Cisler et al., 2010) is a computer-administered protocol in which a stimulus picture (fear facial expression or neutral facial expression) is presented as a cue on either the left side of a computer screen, whose offset either predicts or does not predict the subsequent location of a response probe. There are 132 trials distributed evenly across the following factorial design: 2 (cue type: fear face vs neutral face) x 3 (cue position: opposite to probe, same as probe, center of screen). Each trial lasts 500 ms plus the participants reaction time.

*Reinforcement learning task:* The fear extinction protocol (see below) requires the tracking of associations between stimuli; thus, as a control for generic reinforcement learning, we would have participants complete a reinforcement learning task outside of the scanner. Similar to our other protocol (2016-1307), the task would resemble commonly used decision-making tasks towards the goal of earning as many points as possible. Participants select geometric shapes that are associated with a pre-determined probability of earning or losing points. Additionally, as a distractor, each of the shapes is associated with the appearance of a picture selected from the International Affective Picture System (IAPS), a well-normed and widely used set of pictures. Shapes would be associated with the occurrence of either a negative (e.g., snakes) or neutral (e.g., mountains) picture, as determined by the normed ratings of the IAPS. The points would displayed concurrently with the picture, but have no relationship to the amount of points earned. There would be ~150 trials and the task would take ~8 minutes to complete.

#### Mock MRI scan

During session 1 or session 2, subjects may go to the MRI Simulator room for a mock scan session. In addition, if the subject is particularly anxious, we may ask him/her to participate in an additional mock scan between sessions 1 and 2.

In the lab, the mock scanning room has been designed to very closely enact a neuroimaging procedure with the exception that the scanning apparatus is not capable of generating a magnetic field. The mock scan protocol is critical for the current study, primarily to decrease the novelty of the experimental procedures, which is especially important for patients with anxiety. Importantly, it also allows for a practice session prior to data collection. The participants will hear an audio file that replicates the scanner noise that occurs during the real scanning session. The subject will be able to see images through goggles or a mirror that are similar to those they will see during the actual scan. Study personnel will support and coach subjects if they have any difficulties accommodating to the scanner environment. During this mock practice session the importance of keeping the head still during the scan is emphasized, and participants have a chance to practice this.

#### MRI Procedures

Before the MRI scan, participants will be given an explanation of the study's procedures and screened with the MRI Safety Screening Form for metal objects and claustrophobia. The participant will then lie supine in the scanner. Participants will wear ear plugs and noise-

cancelling headphones for communication and view visual stimuli through a mirror attached to the imaging head coil. Participants will undergo an anatomic scan in order to acclimate to the MRI environment. The order of the tasks will be counterbalanced.

All participants will be asked to leave a urine sample prior to the scan. The sample would be tested for tobacco and drugs of abuse as well as to confirm lack of pregnancy. Heart rate, respiration, and galvanic skin response will be measured during the scan using the BIOPAC physiology monitoring system. A plethsmograph (rubber band) placed around the subject's fingernail will measure heart rate via changes in blood oxygenation beneath the cuticle. A flexible respiration transducer (rubber belt) around the subject's abdomen will measure expansions and contractions as the subject breathes. Electrodes placed upon the subject's skin will measure galvanic skin response.

*Generic fear conditioning and extinction task.* This fMRI task (Haaker, Gaburro, Sah, Gartmann, Lonsdorf, Meier, Singewald, Pape, Morellini, & Kalisch 2013a; Phelps, Delgado, Nearing, & LeDoux 2004) is divided into three distinct phases: fear acquisition, fear extinction, and recall. The unconditioned stimulus (UCS) would be an electrotactile stimulation delivered to the left wrist using our MRI compatible BIOPAC equipment. The intensity of the stimulation would be set prior to the experiment for each participant as a level that is "unpleasant but not painful," a procedure that is commonly used in the literature (Haaker et al. 2013b; Phelps, Delgado, Nearing, & LeDoux 2004). Participants would use the Electrotactile Stimulation Calibration form to rate the degree of unpleasantness.

In the fear acquisition phase, participants would be presented, in an alternating fashion, with two geometric shapes (triangle and circle) for 3 s duration (3-6 s ITI). One shape would be the CS+ whose offset overlaps (at 2.5 s) with presentation of the UCS with a 50% probability. The other shape would be the CS- and never paired with the UCS. The fear conditioning phase would occur in Context A (with the target stimuli presented against a yellow background).

The fear extinction phase would occur in Context B (with the target stimuli presented against a blue background), during which the CS+ is no longer followed by the UCS. The shapes and background would be counterbalanced as CS+, CS-, Context A, and Context B.

The recall phase occurs ~24 hours later on Day 2, during which participants are presented with the CS+ and CS- alternating between Contexts A and B in a pseudorandom manner, and no presentations of the UCS. The alternation between the contexts allows for testing resistance to context renewal of the fear memory. Every fourth trial, participants also provide self-report ratings of the anxiety elicited from the CS+ and CS- and expectation of the UCS following each CS using a Likert Scale of 0-10. In each phase, there are 12 presentations of the CS+ and CS-.

*Resting task.* The connectivity of the mesolimbic dopaminergic system will be investigated using a standard resting state task, in which participants lie passively in the scanner for 7 minutes and are simply told to let their mind wander freely.

*Characterization of Endogenous Dopamine Neurotransmission and Genetic Analysis.* Following prior studies (Monte-Silva, Liebetanz, Grundey, Paulus, & Nitsche 2010; Pearson-Fuhrhop, Minton, Acevedo, Shahbaba, & Cramer 2013), we would characterize endogenous dopamine neurotransmission via a combined gene score across the following genes: COMT (rs4680), DAT (rs28363170), DRD1 (rs4532), DRD2 (rs1800497), and DRD3 (rs6280). Catechol-o-methyltransferase (COMT) is a catecholamine degrading enzyme. A valmet polymorphism (rs4680) results in ~4 times less enzyme activity and therefore higher baseline dopamine levels. Dopamine transporter protein (DAT) removes synaptic dopamine. The 9-repeat allele of the DAT gene (rs28363170) is associated with less DAT protein and accordingly greater synaptic dopamine levels. DRD1-3 are dopamine receptors. The DRD1 gene has an A/G SNP (rs4532), where the G allele is associated with increased dopamine levels. The DRD2 gene has a polymorphism characterized by a Glu to Lys substitution (rs1800497) that results in ~40% reduction in D2 receptors and reduced D2 binding. The DRD3 gene has a Ser to Gly substitution (rs6280) associated with higher affinity to dopamine. Consistent with prior studies, the presence of COMT valmet allele, DAT 9-repeat allele, DRD1 G allele, DRD2 Glu allele, and DRD3 Gly allele would all be coded = 1, with other allele presentations coded = 0. Thus, an individual's gene score would be the sum across the 5 genes, creating a range of 0 (lowest endogenous dopamine) to 5 (highest endogenous dopamine). Prior studies using these gene combinations to characterize endogenous dopamine neurotransmission have found additive associations with motor learning and depression symptoms (Monte-Silva, Liebetanz, Grundey, Paulus, & Nitsche 2010; Pearson-Fuhrhop, Minton, Acevedo, Shahbaba, & Cramer 2013). Genes coding dopaminergic function (COMT, DAT, DRD2) have also been implicated in PTSD (Cornelis et al. 2010; Wolf et al. 2014).

Participants would provide blood samples, from which DNA will be extracted from whole blood using the Qiagen Biorobot M48 according to standardized protocols. Single nucleotide polymorphisms (SNPs), such as those in *COMT*, will be genotyped in 384-well format using validated Taqman assays and the 7900 Sequence detection system (ABI). Variable number tandem repeat polymorphisms (VNTRs), such as those in *SLC6A3 (aka DAT1)*, will be genotyped using established assays from the literature (Fuke, Suo, Takahashi, Koike, Sasagawa, & Ishiura, 2001). This assay involves PCR amplification of the region in each subject followed by size discrimination using standard electrophoresis or an Applied Biosystems 3100 genetic analyzer. All variants will be tested for adherence to Hardy-Weinberg Equilibrium, and those that do not will be excluded from further analyses. Approximately, 10 mL of blood will be collected for analysis in standard purple-top vials. In the event an inadequate amount of blood or poor sample is collected, all participants will also provide a saliva sample (approximately 2mL) for genotyping if necessary.

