**PI: [name].**

et al. 2006). In urn randomization, an algorithm modifies ongoing randomization probabilities based on prior composition of treatment groups, maximizing multivariate equivalence of treatment groups (Wei and Lachin 1988). Thus, urn randomization offers the benefits of balancing allocation of important prognostic variables in treatment groups while still retaining the benefits of random assignment (Stout et al. 1994). Participants will be randomized based on comorbid diagnoses, age, and current medication usage.

*Implementation.* The “urn” randomization will be implemented by a department statistician, who will have no direct contact with the participants and no knowledge of the pill assignment to the group labels and thus has negligible chance of biasing the randomization sequence or implementation.

*Blind Assessors.* The clinical research coordinators performing the assessments will be blind to the treatment conditions; thus minimizing the possibility of systematically biasing the assessment procedures.

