### Data analysis.

*Primary Analytic Framework for Fear Extinction Effects.* The overall data analysis framework for Aim 1 fear extinction analyses consists of a 3 (group: placebo vs 100 mg L-DOPA vs 200 mg L-DOPA) x 2 (cue: CS+ vs CS-) x 2 (context: A [learning context] vs B [extinction context]) x 6 (dopamine gene score: 0 [low endogenous dopamine] – 5 [high endogenous dopamine]) mixed design focused on Day 2 fear responding. Preliminary analyses would test for any baseline

differences in fear responding or extinction learning on Day 1 and include these variables as covariates if needed. Analyses would also control for ancestry as well as other demographic or clinical variables should they differ between groups.

*Neural circuit ROI definition and extraction.* The neural circuit indices would be 6 *a priori* regions of interest (ROI) with anatomical coordinates defined from the recent literature (Delgado et al. 2008; Haaker, Gaburro, Sah, Gartmann, Lonsdorf, Meier, Singewald, Pape, Morellini, & Kalisch 2013a; Milad, Wright, Orr, Pitman, Quirk, & Rauch 2007; Phelps, Delgado, Nearing, & LeDoux 2004; Schiller et al. 2008) and include bilateral amygdala, bilateral hippocampus, ventromedial PFC, dorsal anterior cingulate cortex. Following standard preprocessing, first-level analyses conducted for each individual separately would consist of whole-brain GLMs, in which the task design (CS+ vs CS- during Context A vs B) is modeled as boxcar events convolved with a canonical HRF. The task design is regressed onto each voxel's timecourse within a GLM framework and using restricted maximum likelihood to account for serial correlation, resulting in a whole-brain spatial map indicating the degree to which each voxel responds to CS+ vs CS- during Context A vs B. The mean contrast values for CS+ vs CS- as a function of context is then extracted from the voxels within 6 mm spherical ROIs for the six ROIs. These analyses would provide six (for each ROI) indices of activation, calculated separately for each participant, that would be used in multivariate analysis of variance (MANOVA) analyses to define the impact of L-DOPA and dopamine gene score on consolidation of fear extinction learning.

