**Planned Fear Extinction Analyses:** We would conduct three sets of MANOVA analyses, one with the set of Day 2 neural circuit indices (amygdala, dorsal anterior cingulate cortex, caudate) as dependent variables, one with the set of Day 2 physiological indices (SCR, HR, HRV) as dependent variables, and one with the set of Day 2 verbal/self-report indices (anxiety, UCS expectation) as dependent variables. In these analyses, the mixed effects of L-DOPA group, dopamine gene score, cue, context, and the interactions are entered as factors explaining variance in the multivariate combination of the set of dependent variables. Interactions with context would demonstrate the effect of the manipulations on robustness to context renewal effects. Additionally, any factors that differ between groups, such as Day 1 fear responding, age, or comorbid diagnoses, would also be entered as covariates should the balanced "urn" randomization fail. Given the three sets of tests, FDR correction (Benjamini and Hochberg 1995) would be used to control for alpha inflation. If the multivariate analyses reveal significant between-group differences in our measures of neural, psychophysiological and/or verbal/self-report, they would be followed up with simple effect testing to identify the specific conditions and measures driving the larger multivariate effect. We would additionally test for linear and quadratic contrasts for the group comparisons in order to establish dose-dependent learning, and its gating by dopamine gene score, effects on these primary DVs. All analyses would be completed prior to breaking the blind in order to minimize bias.

*Defining dopaminergic resting-state functional connectivity (FC).* Following the prior studies cited above (Haaker, Gaburro, Sah, Gartmann, Lonsdorf, Meier, Singewald, Pape, Morellini, & Kalisch 2013a; Kelly, de, Di, Copland, Reiss, Klein, Castellanos, Milham, & McMahon 2009), we

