*Testing the effect of altered resting-state FC on fear extinction learning consolidation.* Following identification of regions where FC with the DC, VS, and SN/VTA differ as a function of the L-DOPA x gene score interaction, we would then test whether individual differences in FC within these clusters predict subsequent consolidation of fear extinction learning. That is, we would test whether the hypothesized intermediate mechanism (acute dopamine neurotransmission and downstream dopaminergic neural networks) is related to the ultimate mechanism of interest (fear extinction learning). Consolidation of fear extinction learning from Day 1 would again be tested using Day 2 fear expression indices in Context A and Context B (i.e., fear extinction learning recall test) using multimodal assessments (neural circuit indices, psychophysiological, and self-report). GLMs would be used in which the outcome variable is regressed simultaneously onto the FC cluster, L-DOPA group, dopamine gene score, cue, and context. This would be repeated for the separate fear expression indices, with FDR controlling for alpha inflation due to multiple comparisons. These analyses would identify the clusters of voxels whose FC with the VS, DC, and SN/VTA predict enhanced recall on Day 2.

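### Shape and colour roles are counterbalanced in the task but appear in no Day 2 model, so any stimulus effect stays in the error of the cue and context contrasts

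*Combined protocol and SAP*

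**What the plan says.** The task description (section C, MRI Procedures) presents "two geometric shapes (triangle and circle) for 3 s duration (3-6 s ITI"), with yellow and blue backgrounds marking the two contexts, and states that "The shapes and background would be counterbalanced as CS+, CS-, Context A, and Context B". It does not give the number of versions, how a woman is assigned to one, or whether assignment is tied to drug group.

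Section C, Balanced Randomization, lists the urn factors: "Participants will be randomized based on comorbid diagnoses, age, and current medication usage". Task version is not among them.

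Section G, Planned Fear Extinction Analyses, defines the Day 2 MANOVAs, in which "the mixed effects of L-DOPA group, dopamine gene score, cue, context, and the interactions are entered as factors". For the neural indices, "The mean contrast values for CS+ vs CS- as a function of context is then extracted" from each region. The later Day 2 GLMs, which relate resting-state connectivity to extinction recall, are specified so that "the outcome variable is regressed simultaneously onto the FC cluster, L-DOPA group, dopamine gene score, cue, and context". None of these has a term for shape or colour role.

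Two covariate rules apply. The primary analytic framework says "Analyses would also control for ancestry as well as other demographic or clinical variables should they differ between groups". The planned analyses are wider: should the urn randomisation fail, "any factors that differ between groups, such as Day 1 fear responding, age, or comorbid diagnoses, would also be entered as covariates".

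**The concern.** Counterbalancing makes a stimulus effect average out over the sample. It does not remove that effect from any one woman's score. If triangles provoke more response than circles whatever their role, a woman whose CS+ is the triangle has a larger CS+ minus CS- difference, and a woman whose CS+ is the circle has a smaller one. The same holds for background colour and the Context A minus B difference. With no term for these roles, the spread counts as unexplained variation between women in the cue and context contrasts, and in the interactions of those contrasts with L-DOPA group and gene score. The source of this variation is known and fixed by design, so leaving it in the error gives away precision for no return. The plan claims only about 0.8 power for medium-large effects, so there is not much to spare.

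**Working it through.** **1. Where stimulus effects go.** Code shape role a = ±1, colour role b = ±1, cue = +1 for CS+ and -1 for CS-, context = +1 for A and -1 for B. Let s be the shape effect, c the colour effect and q their interaction. The stimulus part of a response is s·a·cue + c·b·context + q·a·b·cue·context. Averaging over a woman's four cells with the contrast signs gives:

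| Contrast | Stimulus contribution |
|---|---|
| Cue (CS+ vs CS-) | ±s |
| Context (A vs B) | ±c |
| Cue x context | ±q only |
| Woman's mean | 0 |

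For the region-of-interest indices, which are already CS+ minus CS- within a context, the colour main effect drops out. What remains is ±s plus the interaction q. The four versions come from 2 shapes x 2 colours and are an inference; the documents do not give the number.

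**2. The plan's power figure.** Inputs: 35 per group and N = 105 (section G). Alpha 0.05 is assumed, as none is stated. A one-way ANOVA with 3 groups gives power 0.96 at f = 0.40 and 0.80 at f = 0.307. This matches the plan's statement if its large effect is f = 0.40 and its medium-large effect is about f = 0.31. The plan gives no numeric effect size, so this is only a consistency check.

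**3. Loss from omitting the role terms.** Let r be the ± stimulus effect on the contrast divided by the contrast's within-version SD. Omission multiplies the error variance by 1 + r², so f becomes 0.307/√(1 + r²). Version then accounts for r²/(1 + r²) of the variance.

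| r (assumed) | Variance share | Power, roles omitted |
|---|---|---|
| 0.1 | 1.0% | 0.796 |
| 0.2 | 3.8% | 0.783 |
| 0.3 | 8.3% | 0.763 |
| 0.5 | 20% | 0.700 |

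With the roles modelled (3 df, error df 99 instead of 102) power is 0.80 in every row. If the planning effect size was already scaled to an SD that contains the version effect, the gain is measured upwards from 0.80 instead: 0.816, 0.835 and 0.884 at r = 0.2, 0.3 and 0.5.

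**4. Type I error (simulated, three arms of 35).** With versions assigned independently of arm and not modelled, it is 0.045, 0.052 and 0.050 at r = 0.3, 0.5 and 1.0, so there is no inflation. With versions balanced within arm and not modelled, it is 0.039, 0.027 and 0.002, which is conservative.

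**5. Break-even.** The net gain in effective sample size from 3 df is [1/(1 - v)] x (99/102), where v is the share of variance explained. This gives 1.00, 1.02, 1.08 and 1.14 at v = 3%, 5%, 10% and 15%. It equals 1 at v = 3/102, about 3%.

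**6. Chance imbalance, if assignment ignores arm.** The SD of the difference between two arms in the share with a given shape as CS+ is √(2 x 0.25/35) = 0.12. A gap of 20 points or more has probability 0.12 for one pair of arms and 0.27 for at least one of the three pairs.

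**The case against.** The strongest reply is that counterbalancing already does its main job, which is to remove the average confound, and that what remains is an optional covariate of unknown worth. The documents contain nothing to show that a triangle/circle or yellow/blue effect exceeds the 3% break-even. The wider covariate rule speaks of any factors that differ between groups, so version could enter if the arms were unequal on it. A Day 1 fear-responding covariate, measured with the same stimuli, might absorb part of the effect.

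Much of this stands. The size is unknown, and the covariate rule does reach imbalance in principle. But that rule does not name version, depends on the urn randomisation failing, and recovers no precision when versions happen to be even across arms. That is also the case in which the unmodelled test is conservative.

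A reader might infer three stronger things, and the documents support none of them:

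- **Versions are unbalanced across arms.** The protocol is silent on assignment; it neither describes nor rules out balancing.
- **The L-DOPA comparisons are biased or their type I error inflated.** Under independent assignment, chance imbalance is already reflected in the standard error, as step 4 shows.
- **Every planned contrast is affected.** Shape and colour main effects cancel in the renewal contrast and in each woman's mean, so overall L-DOPA and gene-score effects on response level are not widened. The resting-state connectivity measures involve no shapes or backgrounds.

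**Conclusion.** The point holds as a minor matter of precision. Shape and colour role are known design factors, and no prespecified Day 2 model contains them. Any stimulus main effect therefore widens the error of the cue and context contrasts and of their interactions with L-DOPA group and gene score.

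The size rests on assumed values of r: from 0.80 power, under 2 points at r up to 0.2, about 4 at r = 0.3 and about 10 at r = 0.5. These figures also assume alpha 0.05 and a simple three-arm comparison of one contrast per woman, before the planned FDR correction. They do not show the plan's power statement to be wrong.

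The case for acting is the lopsided trade. Modelling the roles costs at most about 1 power point if the stimuli have no effect, while leaving them out can cost several points if they do.

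**What to change.** Prespecify shape role and colour role in the Day 2 MANOVAs and in the Day 2 GLMs on connectivity and recall, whether or not the arms differ on them. Where the data are kept by cue and context, enter the roles with their within-woman interactions: shape role x cue, colour role x context, and the product of the two roles for cue x context. A between-woman version term alone would act on the woman's mean, where these effects already cancel, so it would recover nothing. Where the outcome is already a CS+ minus CS- difference, as for the region-of-interest indices, enter the roles directly as covariates.

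State in the protocol how many versions there are and how they are assigned. For women still to be enrolled, rotate versions within each colour-labelled randomisation group and within site. The statistician who runs the urn works only with the labels, so this need not touch the blind.

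The cost is 1 to 3 degrees of freedom and no new measurement. With all 3 df spent, the change breaks even at about 3% of variance explained.
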